9.1.4 End of Study

The EOS visit will occur 18 weeks after the EOT visit (20 weeks after the final dose of study drug) and is the same as the safety follow-up visit.

9.2 Description of General Study Assessments and Procedures

The sections below provide a description of the individual study procedures for required time points.

9.2.1 General Assessments

Study procedures and their timing are discussed in the Schedule of Activities ([Table 2-1](#) and [Table 2-2](#)).

9.2.1.1 Informed Consent

All subjects or their legally authorized representative must sign and personally date the IRB/IEC approved informed consent before any study-specific procedures are performed.

9.2.1.2 Demographics

Demographic data collection including sex, age, race, and ethnicity will be collected in order to study their possible association with subject safety and treatment effectiveness. Additionally, demographic data will be used to study the impact on biomarker variability and PK of the protocol-required therapies.

9.2.1.3 Medical History

The Investigator or designee will collect a complete medical history that started within 5 years prior to enrollment through informed consent. Medical history will include information on the subject's concurrent medical conditions. Record all findings on the medical history CRF. In addition to the medical history above, AD history must date back to the original diagnosis. The current severity will be collected for each condition that has not resolved.

9.2.1.4 Physical Examination

Physical examination will be performed as per standard of care. Physical examination findings should be recorded on the appropriate CRF (eg, medical history, event).

9.2.1.5 Physical Measurements

Height in centimeters should be measured without shoes. Weight in kilograms should be measured without shoes.

9.2.1.6 Substance Use

Obtain a detailed history of use of alcohol, tobacco, and caffeine.

9.2.2 Efficacy Assessments

9.2.2.1 Investigator's Global Assessment

The IGA allows investigators to assess overall disease severity at 1 given time point and consists of a 5-point severity scale from clear to severe disease (0 = clear; 1 = almost clear; 2 = mild disease; 3 = moderate disease; 4 = severe disease; 5 = very severe disease). The IGA uses clinical characteristics of erythema, infiltration, papulation, oozing, and crusting as guidelines for the overall severity assessment (Breuer et al, 2004). The IGA will be assessed at every visit according to the Schedule of Activities (Table 2-1 and Table 2-2). Whenever possible, the IGA should be assessed by the same investigator at each visit to reduce inter-rater variability.

9.2.2.2 Eczema Area and Severity Index

The EASI was designed by modifying the Psoriasis Area and Severity Index, which has been widely used in clinical trials and has been established as a well-accepted and standardized instrument for assessing therapeutic response in patients with psoriasis (Schmitt et al, 2007). The EASI evaluates 4 natural anatomical regions for severity and extent of key disease signs and focuses on key acute and chronic signs of inflammation (ie, erythema, induration/papulation, excoriation, and lichenification). The maximum score is 72, with higher values indicating more severe disease.

The EASI will be assessed at every visit according to the Schedule of Activities (Table 2-1 and Table 2-2). Whenever possible, the EASI should be assessed by the same investigator at each visit to reduce the inter-rater variability.

9.2.2.3 Scoring of Atopic Dermatitis

The SCORAD is a clinical tool for assessing the severity (ie, extent, intensity) of AD. The tool evaluates the extent and intensity of the AD lesions, along with subjective symptoms (Kunz et al, 1997). The maximum total score is 103, with higher values indicating more severe disease. The SCORAD should be assessed by the same investigator at each visit, whenever possible, to reduce inter-rater variability. The SCORAD will be conducted according to the Schedule of Activities (Table 2-1 and Table 2-2).

9.2.2.4 Patient-reported Outcomes

The electronic diary (eDiary), which includes the pruritus NRS, will be completed by the subject at home each morning during the treatment and follow-up periods. The remaining PROs will be conducted at the study center at the visits specified in the Schedule of Activities ([Table 2-1](#) and [Table 2-2](#)) and should be completed prior to other study assessments to avoid the possibility of introducing bias to subject responses.

9.2.2.4.1 Electronic Diary

The electronic diary includes 1 item to capture subject-reported pruritus. The diary will be completed by the subject at home each morning using an electronic device according to the Schedule of Activities ([Table 2-1](#) and [Table 2-2](#)).

9.2.2.4.1.1 Pruritus Numeric Rating Scale

Pruritus will be assessed using an NRS (0-10) with 0 = no itch and 10 = worst imaginable itch. Subjects will complete the NRS as part of the daily diary each day in the morning according to the Schedule of Activities ([Table 2-1](#) and [Table 2-2](#)).

9.2.2.4.2 Patient Oriented Eczema Measure

The Patient Oriented Eczema Measure (POEM) is a 7-item validated questionnaire used in clinical practice and clinical trials to assess disease symptoms in children and adults ([Charman, 2004](#)). It evaluates time spent in the past week with AD signs and symptoms: individual items of itching, bleeding, oozing, cracked, flaking, and dry/rough skin, and their impact on sleep. The POEM will be assessed at the study center, according to the Schedule of Activities ([Table 2-1](#) and [Table 2-2](#)).

9.2.2.4.3 Dermatology Quality of Life Index

The DLQI is a 10-item, subject-completed, HRQoL assessment with content specific to those with dermatology conditions. The recall period is 1 week ([Finlay and Kahn, 1994](#)). The DLQI content captures respondent perceptions of dermatology-related symptoms and feelings (embarrassment), impacts on daily activities, leisure, work or school, personal relationships, and the side effects of treatment. Each item is scored on a 4-point Likert scale: 0 = not at all/not relevant; 1 = a little; 2 = a lot; and 3 = very much ([Basra et al, 2008](#)). The DLQI will be completed by the subject at the study center according to the Schedule of Activities ([Table 2-1](#) and [Table 2-2](#)).

9.2.2.4.4 Patient Global Impression of Severity

The PGI-S is a single item designed to capture the subject's perception of overall symptom severity at the time of completion on a 5-point categorical response scale

(no symptoms to very severe symptoms. The PGI-S will be completed by the subject at the study center according to the Schedule of Activities ([Table 2-1](#) and [Table 2-2](#)).

9.2.3 Safety Assessments

Planned time points for all safety assessments are listed in the Schedule of Activities.

9.2.3.1 Adverse Events

All adverse events observed by the investigator or reported by the subject that occur after the first dose of investigational product through the end of study/safety follow-up visit or 20 weeks after the last administration of investigational product are to be collected/reported.

All adverse events related to any study procedure/activities will be collected/reported after signing the informed consent form through the end of study/safety follow-up visit or 20 weeks after the last dose of investigational product.

9.2.3.1.1 Time Period and Frequency for Collecting and Reporting Safety Event Information

9.2.3.1.1.1 Disease-related Events

Disease-related events are defined in [Appendix 4](#).

The investigator is responsible for ensuring that all disease-related events observed by the investigator or reported by the subject that occur after the first dose of investigational product(s)/study treatment/protocol-required therapies through the end of study are recorded using the Event CRF.

All serious disease-related events will be recorded and reported to the sponsor or designee within 24 hours. The investigator will submit any updated serious disease-related event data to the sponsor within 24 hours of it being available.

Disease-related events assessed by the investigator to be more severe than expected and/or related to the investigational product(s)/study treatment/protocol-required therapies, and determined to be serious, must be reported on the Event CRF as serious adverse events and recorded and reported per [Appendix 4](#) and [Section 9.2.3.1.1.3](#).

Disease-related events pre-defined for this study include AD.

9.2.3.1.1.2 Adverse Events

The adverse event grading scale to be used for this study will be the Common Terminology Criteria for Adverse Events (CTCAE), version 5.0 and is described in [Appendix 4](#).

The investigator is responsible for ensuring that all adverse events observed by the investigator or reported by the subject that occur after first dose of investigational product(s)/study treatment/protocol-required therapies through the end of study are reported using the Event CRF.

9.2.3.1.1.3 Serious Adverse Events

The investigator is responsible for ensuring that all serious adverse events observed by the investigator or reported by the subject that occur after signing of the informed consent through 20 weeks after the last administration of investigational product are reported using the Event CRF.

All serious adverse events will be collected, recorded and reported to the sponsor or designee within 24 hours, as indicated in [Appendix 4](#). The investigator will submit any updated serious adverse event data to the sponsor within 24 hours of it being available.

The criteria for grade 4 in the CTCAE grading scale differs from the regulatory criteria for serious adverse events. It is left to the investigator's judgment to report these grade 4 abnormalities as serious adverse events.

9.2.3.1.1.4 Serious Adverse Events After the Protocol-required Reporting Period

There is no requirement to monitor study subjects for serious adverse events following the protocol-required reporting period or after end of study. However, these serious adverse events can be reported to Amgen. Per local requirements in some countries, investigators are required to report serious adverse events that they become aware of after end of study. If serious adverse events are reported, the investigator is to report them to Amgen within 24 hours following the investigator's knowledge of the event.

Serious adverse events reported outside of the protocol-required reporting period will be captured within the safety database as clinical trial cases and handled accordingly based on relationship to investigational product.

The method of recording, evaluating, and assessing causality of adverse events, adverse device effects, disease-related events, and serious adverse events and the procedures for completing and transmitting serious adverse event reports are provided in [Appendix 4](#).

9.2.3.1.2 Method of Detecting Adverse Events and Serious Adverse Events

Care will be taken not to introduce bias when detecting adverse events and/or serious adverse events. Open-ended and non-leading verbal questioning of the subject is the preferred method to inquire about adverse event occurrence.

9.2.3.1.3 Follow-up of Adverse Events and Serious Adverse Events

After the initial adverse event/serious adverse event report, the investigator is required to proactively follow each subject at subsequent visits/contacts. All adverse events and serious adverse events will be followed until resolution, stabilization, until the event is otherwise explained, or the subject is lost to follow-up (as defined in [Section 8.3](#)).

Further information on follow-up procedures is given in [Appendix 4](#).

All new information for previously reported serious adverse events must be sent to Amgen within 24 hours following knowledge of the new information. If specifically requested, the investigator may need to provide additional follow-up information, such as discharge summaries, medical records, or extracts from the medical records.

Information provided about the serious adverse event must be consistent with that recorded on the Event CRF.

9.2.3.1.4 Regulatory Reporting Requirements for Serious Adverse Events

If subject is permanently withdrawn from protocol-required therapies because of a serious adverse event, this information must be submitted to Amgen.

Prompt notification by the investigator to the sponsor of serious adverse events is essential so that legal obligations and ethical responsibilities towards the safety of subjects and the safety of a study treatment under clinical investigation are met.

The sponsor has a legal responsibility to notify both the local regulatory authority and other regulatory agencies about the safety of a study treatment under clinical investigation. The sponsor will comply with country-specific regulatory requirements relating to safety reporting to the regulatory authority, IRB/IECs, and investigators.

[figure not shown]
Individual safety reports must be prepared for suspected unexpected serious adverse reactions (SUSAR) according to local regulatory requirements and sponsor policy and forwarded to investigators as necessary.

An investigator who receives an individual safety report describing a serious adverse event or other specific safety information (eg, summary or listing of serious adverse events) from the sponsor will file it along with the Investigator's Brochure and will notify the IRB/IEC/IEC, if appropriate according to local requirements.

To comply with worldwide reporting regulations for serious adverse events, the treatment assignment of subjects who develop serious, unexpected, and related adverse events may be unblinded by Amgen before submission to regulatory authorities. Aggregate analyses may also be unblinded by the Safety Assessment Team (SAT) as appropriate. Investigators will receive notification of related serious adverse events reports sent to regulatory authorities in accordance with local requirements.

9.2.3.1.5 Events of Interest

An event of interest (EOI) is an event of scientific and medical interest towards improving the understanding of the investigational product. An EOI may be serious or non-serious. For this study, EOIs include:

9.2.3.1.6 Pregnancy and Lactation

Details of all pregnancies and/or lactation in female subjects and female partners of male subjects will be collected after the start of study treatment and until **16** weeks after the final dose of study drug or the final study visit, whichever occurs later.

If a pregnancy is reported, the investigator is to inform Amgen within 24 hours of learning of the pregnancy and/or lactation and is to follow the procedures outlined in [Appendix 5](#). Amgen Global Patient Safety will follow-up with the investigator regarding additional information that may be requested.

Abnormal pregnancy outcomes (eg, spontaneous abortion, fetal death, stillbirth, congenital anomalies, ectopic pregnancy) are considered serious adverse events.

Further details regarding pregnancy and lactation are provided in [Appendix 5](#).

9.2.3.2 Vital Signs

The following measurements must be performed: systolic/diastolic blood pressure, heart rate, respiratory rate, and temperature. Subject must be in a supine position in a rested and calm state for at least 5 minutes before blood pressure assessments are conducted. If the subject is unable to be in the supine position, the subject should be in most recumbent position as possible. The position selected for a subject should be the same that is used throughout the study and documented on the vital sign CRF. The temperature location selected for a subject should be the same that is used throughout the study and documented on the vital signs CRF. Record all measurements on the vital signs CRF.

9.2.3.3 Electrocardiograms (ECGs)

Subject must be in supine position in a rested and calm state for at least 5 minutes before ECG assessment is conducted. If the subject is unable to be in the supine position, the subject should be in most recumbent position as possible. The ECG must include the following measurements: Heart Rate, QRS, QT, QTc, and PR intervals. The principal investigator (PI) (or designated study center physician or central reader) will review all ECGs. Once signed, the original ECG tracing will be retained with the subject's source documents. At the request of the sponsor, a copy of the original ECG will be made available to Amgen.

9.2.3.4 Suicidal Risk Monitoring

Suicidal risk monitoring is not required for tezepelumab.

9.2.3.5 Other Safety

There are no other safety considerations for this study.

9.2.4 Clinical Laboratory Assessments

Refer to [Appendix 2](#) for the list of clinical laboratory tests to be performed and to the Schedule of Activities for the timing and frequency.

The investigator is responsible for reviewing laboratory test results and recording any clinically relevant changes occurring during the study in the Event CRF. The investigator must determine whether an abnormal value in an individual study subject represents a clinically significant change from the subject's baseline values. In general, abnormal laboratory findings without clinical significance (based on the investigator's judgment) are not to be recorded as adverse events. However, laboratory value changes that require treatment or adjustment in current therapy are considered adverse events.

Where applicable, clinical sequelae (not the laboratory abnormality) are to be recorded as the adverse event.

All protocol-required laboratory assessments, as defined in [Appendix 2](#), must be conducted in accordance with the laboratory manual and the Schedule of Activities.

Laboratory/analyte results that could unblind the study will not be reported to investigative study centers or other blinded personnel until the study has been unblinded. Only eosinophils on complete blood count and differential are considered unblinding data for this study. Additional details regarding potentially unblinding data and study personnel are provided in [Section 7.3.2](#).

9.2.4.1 Tuberculosis Testing

All subjects must receive either a purified protein derivate (PPD) or Quantiferon test at screening and ET/EOT.

The PPD test must be read by a trained healthcare professional 48 to 72 hours after the test is placed. PPD reader must be identified on the delegation of authority for this responsibility.

If a subject does not receive a PPD test, they must have Quantiferon testing. Refer to the central laboratory manual for instructions on sample collection, processing, and shipping of samples.

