2.2 Schedule of Activities

Table 2-1. Schedule of Activities for Part A and Part B (Screening Through Week 24)

	Screening ^a (up to -28 d + 7 d)	Treatment Period (52 weeks) ^{b, p}													
		Day 1	Wk 2	Wk 4	Wk 6	Wk 8	Wk 10	Wk 12	Wk 14	Wk 16	Wk 18	Wk 20	Wk 22	Wk 24	
GENERAL AND SAFETY ASSESSMENTS															
Informed consent	X														
Informed consent for optional biomarker/pharmacogenetic assessments	X														
Verify eligibility criteria	X	X ^o													
Demographics	X														
Physical examination	X														
Physical measurements	X														
Medical and dermatology history	X														
Randomization		X													
Substance use	X														
12-lead ECG ^c	X														
Vital signs ^d	X	X	X	X	X	X	X	X	X	X	X	X	X	X	X
Adverse events		X	X	X	X	X	X	X	X	X	X	X	X	X	X
Serious adverse events	X	X	X	X	X	X	X	X	X	X	X	X	X	X	X
Disease-related events	X	X	X	X	X	X	X	X	X	X	X	X	X	X	X
Concomitant therapies review		X	X	X	X	X	X	X	X	X	X	X	X	X	X
LABORATORY ASSESSMENTS															
Serum or urine pregnancy test ^e	X	X		X		X		X		X		X		X	
Coagulation	X	X							X						
Hematology	X	X						X							X
Chemistry	X	X						X							X
HIV, Hepatitis B and C screening	X														
Urinalysis (dipstick)	X	X						X							X
Anti-tezepelumab-antibody		X						X							X
Serum immunoglobulins ^f	X	X								X					

Footnotes defined on last page of the table

Table 2-1. Schedule of Activities for Part A and Part B (Screening Through Week 24)

	Screening ^a (up to -28 d + 7 d)	Treatment Period (52 weeks) ^{b, p}													
		Day 1	Wk 2	Wk 4	Wk 6	Wk 8	Wk 10	Wk 12	Wk 14	Wk 16	Wk 18	Wk 20	Wk 22	Wk 24	
PPD or Quantiferon GOLD	X														
STUDY-SPECIFIC ASSESSMENTS															
eDiary device distribution and training	X														
Electronic diary ⁹	Completed in the morning at home on eDiary														
Assessment of EASI and IGA	X	X		X	X	X	X	X		X				X	
SCORAD		X		X		X		X		X				X	
EQ-5D-3L, POEM, DLQI, PGI-S		X		X		X		X		X				X	
Tracking of TCS use (Part B subjects only)	X	X	X	X	X	X	X	X	X	X	X	X	X	X	
PHARMACOKINETIC ASSESSMENTS															
PK sampling ^k		X	X ⁱ	X ⁱ				X		X				X ⁱ	
PHARMACOGENETIC ASSESSMENTS															
Sample for DNA analysis (optional)		X													
STUDY TREATMENT															
Administration of tezepelumab or placebo ^m		X ⁿ	X	X	X	X	X	X	X	X	X	X	X	X	

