5.4 Justification for Investigational Product Dose

[REDACTED]

[REDACTED]

[REDACTED]

[REDACTED]

[REDACTED]

[REDACTED]

[REDACTED]

[REDACTED]

[REDACTED]

[REDACTED]

[REDACTED]

[REDACTED]

[REDACTED]

[REDACTED]

[REDACTED]

[REDACTED]

[REDACTED]

[REDACTED]

[REDACTED]

[REDACTED]

[REDACTED]

[REDACTED]

[REDACTED]

[REDACTED]

[REDACTED]

[REDACTED]

6. Study Population

Investigators will be expected to maintain a screening log of all potential study candidates that includes limited information about the potential candidate (eg, date of screening). This log may be completed and updated via an Interactive Voice Response System (IVRS)/Interactive Web Response System (IWRS).

Eligibility criteria will be evaluated during screening. Each subject should meet all the inclusion criteria and none of the exclusion criteria for this study in order to be enrolled. Under no circumstances can there be exceptions to this rule. Prospective approval of protocol deviations to recruitment and enrollment criteria, also known as protocol waivers or exemptions, is not permitted. Subjects who do not meet the entry requirements for enrollment are screen failures.

Before any study-specific activities/procedures, the appropriate written informed consent must be obtained (see [Appendix 3](#)).

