6.2 Exclusion Criteria

Subjects are excluded from the study if any of the following criteria apply:

Disease Related

- 201 Active dermatologic conditions, which might confound the diagnosis of AD or would interfere with the assessment of treatment, such as scabies, seborrheic dermatitis, cutaneous lymphoma, ichthyosis, psoriasis, allergic contact dermatitis, or irritant contact dermatitis
- 202 History of a clinically significant infection within 28 days prior to day 1 that, in the opinion of the investigator or medical monitor, might compromise the safety of the subject in the study, interfere with evaluation of the investigational product, or reduce the subject's ability to participate in the study. Clinically significant infections are defined as either of the following:
 - 1) a systemic infection; or
 - 2) a serious skin infection requiring parenteral antibiotic, antiviral, or antifungal medication
- 203 Diagnosis of a helminth parasitic infection within 6 months prior to screening that had not been treated with or had failed to respond to standard of care therapy
- 204 Documented medical history of chronic alcohol or drug abuse within 12 months prior to screening
- 205 History of anaphylaxis following any biologic therapy
- 206 Evidence of active liver disease at screening, including jaundice or aspartate aminotransferase (AST), alanine aminotransferase (ALT), or alkaline phosphatase greater than twice the upper limit of normal (ULN)
- 207 Subjects who, in the opinion of the investigator, have evidence of active tuberculosis (TB), either treated or untreated, or a positive QuantiFERON-tuberculosis Gold (QFT-G) test for TB during screening. Subjects with an indeterminate QFT-G may be enrolled if they have ALL of the following:
 - No symptoms of TB: productive, prolonged cough (> 3 weeks); coughing up blood; fever; night sweats; unexplained appetite loss; unintentional weight loss

- No evidence of active TB on chest radiograph within 3 months prior to the first dose of investigational product. Note: Chest radiograph is not part of screening procedure and will be the responsibility of the Investigator as this is outside the scope of this protocol

- 208 Positive hepatitis B surface antigen or hepatitis C antibody serology. Subjects with a history of hepatitis B vaccination without a history of hepatitis B are allowed to enroll in the study.

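### PPD alone satisfies TB screening, but exclusion 207 gives a test-based consequence only to QFT-G, so a positive PPD has no mandatory effect on eligibility

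*Protocol*

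**What the plan says.** Protocol Section 9.2.4.1 makes TB testing a choice between two tests: "All subjects must receive either a purified protein derivate (PPD) or Quantiferon test at screening and ET/EOT". QuantiFERON becomes compulsory only when the skin test is not done: "If a subject does not receive a PPD test, they must have Quantiferon testing". The screening column of Table 2-1 carries the same choice ("PPD or Quantiferon GOLD"), and Table 12-1 in Appendix 2 repeats it. For the skin test, Section 9.2.4.1 sets the reader and the timing: "The PPD test must be read by a trained healthcare professional 48 to 72 hours after the test is placed". It gives no positivity cut-off and no action on a positive reading.

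Exclusion 207 in Section 6.2 is the only criterion that names TB. It excludes a subject whom the investigator considers to have evidence of active TB, "or a positive QuantiFERON-tuberculosis Gold (QFT-G) test for TB during screening". It then sets a conditional route for an inconclusive blood test: "Subjects with an indeterminate QFT-G may be enrolled if they have ALL of the following". The conditions are absence of TB symptoms and no sign of active TB on a recent chest radiograph. PPD does not appear in 207. On the eligibility criteria as a whole, Section 6 says: "Under no circumstances can there be exceptions to this rule".

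**The concern.** The procedure section accepts two tests, and the criterion that uses the result recognizes one. A site that follows the protocol exactly can reach opposite enrollment decisions for two subjects in the same clinical position, depending only on which test it used.

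At stake is the uniform application of a safety criterion across approximately 100 centers in three regions (Section 5.2.2). Enrolling a PPD-positive subject would also break no stated rule. SAP Section 9.3 takes eligibility deviations from the protocol, so such an enrollment would not be counted as one.

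**Working it through.** The plan states no figure on this point and no arithmetic applies. The check sets the testing rule beside the eligibility rule and then looks for a bridging rule elsewhere.

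**Step 1. Can PPD stand alone?** Yes. Section 9.2.4.1 makes QuantiFERON compulsory only when no PPD is done, and Tables 2-1 and 12-1 agree.

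**Step 2. What follows from each result, for a subject whom the investigator does not consider to have active TB?**

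| Screening result | Mandatory consequence | Source |
|---|---|---|
| QFT-G positive | Excluded | Exclusion 207, with Section 6 allowing no exceptions |
| QFT-G indeterminate | May enter only with no TB symptoms and no active TB on chest radiograph | Exclusion 207 |
| QFT-G negative | None | Exclusion 207 |
| PPD positive | None stated | 207 is silent; Section 9.2.4.1 covers reading only |
| PPD negative | None | As above |

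On the text, a positive PPD leads to the same mandatory outcome as a negative one.

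**Step 3. Does another provision supply the missing rule?**

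- *Section 9.1.1* requires screening evaluations to be completed and reviewed, but against the eligibility criteria, which do not mention PPD.
- *Exclusion 207, active TB limb*, rests on the investigator's opinion and concerns active disease. No test result triggers it.
- *Exclusion 231* rests on the opinion of the investigator or the sponsor's physician. It covers conditions other than those already listed, so whether it reaches TB is arguable.
- *Exclusion 202* also rests on opinion. It concerns recent systemic infection or serious skin infection and does not name a TB test.
- *Appendix 2* permits additional tests that the investigator considers necessary. It requires none after a positive PPD.
- *The laboratory manual* is cited in Section 9.2.4.1 for sample collection, processing and shipping, not for eligibility.

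None makes a positive PPD exclude a subject or trigger a second test. By contrast, the next section, 9.2.4.2, has such a rule for pregnancy: a positive urine test leads to a confirmatory serum test.

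**Step 4. Size.** The number of PPD-positive subjects enrolled would be the number screened, times the share screened by PPD alone, times the share of those with a positive PPD and no evidence of active TB, times the share not excluded at discretion or for another reason. The documents give none of these shares. The only bound is planned enrollment, 240 + 60 = 300, so the range is 0 to about 300, which is uninformative.

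**The case against.** The strongest case on the other side is that the practical gap is narrow. The investigator must review every screening evaluation, must exclude where they see evidence of active TB whichever test was used, and may exclude under 231. The unprotected case is therefore a PPD-positive subject whom the investigator has reviewed and judged to have neither active TB nor a condition posing a risk. That is fair, and it limits the weight of the point. It does not remove it: for QFT-G the protocol did not leave the matter to judgment, because a positive result excludes by itself.

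Several stronger readings are tempting, and the documents do not support them.

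- *That the harm is a long untested dosing period.* For a subject who completes treatment, the next scheduled TB test is at week 52, after the last scheduled dose at week 50. A QFT-G-screened subject follows the same schedule, and neither remedy would change it. The interval and the number of doses therefore do not measure this defect. Adverse events are also reviewed at every scheduled treatment visit, and Section 7.4.2.1 allows dosing to be stopped for clinically significant events.
- *That a positive PPD is treated more leniently than an indeterminate QFT-G.* The symptom and radiograph check is indeed not required after a positive PPD. But that check is a route into the study for an inconclusive result, so the comparison is secondary. The like-for-like contrast is positive PPD against positive QFT-G.
- *That an unread PPD could pass.* Section 9.1.1 requires screening evaluations to be completed.
- *That enrolled subjects face a known TB risk from the drug.* The visible text does not say so. Section 3.3 reports no identified risks to date, and the text that follows is redacted, as is the list of events of interest.

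**Conclusion.** The inconsistency is real and should be corrected. It goes beyond missing detail: followed exactly, the protocol excludes a subject without evidence of active TB who has a positive QFT-G, yet allows enrollment and dosing of a comparable subject with a positive PPD. Only discretionary safeguards stand between that second subject and entry.

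The conclusion rests on two assumptions: that some sites will use PPD alone, as the text permits, and that no document outside those supplied, such as site instructions, already fixes the consequence of a positive PPD. No redaction is apparent in exclusion 207, Section 9.2.4.1 or Table 12-1 that would hide such a rule.

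The number of subjects affected and the clinical harm cannot be judged from the documents. This is an eligibility and safety correction; it does not touch power, alpha, the endpoints or the planned analyses.

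**What to change.** Align exclusion 207 with the permitted tests. Amend its test limb to read: *a positive QFT-G or positive PPD test for TB during screening*. State the PPD positivity cut-off in Section 9.2.4.1. The documents give no cut-off, so the sponsor must choose one; a lower induration threshold will exclude more subjects. The change is a few words and one sentence, needs no new procedure, and applies to subjects screened after it takes effect. Its cost is an unquantified, presumably small, number of additional screen failures, who cannot be rescreened under Sections 6.4 and 9.1.1.

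Alternatively, add one sentence to Section 9.2.4.1 requiring a QFT-G within the same screening period after a positive PPD, with 207 applied to that result. This leaves 207 as it stands and avoids excluding on the skin test alone. It costs one extra blood test per PPD-positive subject and some added exclusions where the QFT-G is positive. An indeterminate result would also call for a chest radiograph, on which 207 says: "Chest radiograph is not part of screening procedure and will be the responsibility of the Investigator".

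Timing also matters under this option. A PPD read 2 to 3 days after placement leaves 7 − 3 = 4 to 7 − 2 = 5 days if placed 7 days before day 1, but only 3 − 3 = 0 to 3 − 2 = 1 day if placed 3 days before. QFT-G turnaround is not stated, so the sentence should set a latest placement day.

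Neither option changes the sample size, endpoints or analysis.
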